#### **8.2.5.1 Statistical Methods for Efficacy Analyses**

Efficacy will be available for PD-L1 strongly positive subjects, PD-L1 positive subjects, and all subjects. The first 100 study subjects (biomarker discovery population) will be evaluated for biomarker cut-point determination. The biomarker discovery population will be excluded from the primary and secondary objectives for the PD-L1 strongly positive subjects.

For the primary efficacy endpoint, the ORR based on RECIST 1.1 by independent radiology review, the point estimate, and 95% confidence interval (as determined by the upper and lower 97.5% one-sided confidence bounds) will be provided using an exact binomial distribution (Clopper and Pearson method). Subjects without response data will be counted as non-responders.

Duration of responses (DOR) based on RECIST 1.1 by independent radiology review will be summarized descriptively using Kaplan-Meier medians and quartiles. Only the subset of subjects who show a complete response or partial response will be included in this analysis. For PFS and OS, Kaplan-Meier (KM) curves, median estimates, and survival rates at 6 and 12 months based on the KM curves (95% CI is based on Greenwood's formula) will be

provided. Subjects without efficacy evaluation data or without survival data will be censored at Day 1.

A summary of the primary analysis strategy for the primary and secondary efficacy endpoints is provided in [Table 8](#).

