### **8.2.5.3 Statistical Methods for Biomarker Analyses**

The evaluation of a general positive association between CPS and ORR will be investigated via standard logistic regression as well as generalized additive models. The potential to achieve a cut-off greater than CPS = 1% for defining a PD-L1 strongly positive population will involve a review of how the positive predictive value (PPV, response rate in those above a cut-off), negative predictive value (NPV, non-response rate in those below the cut-off), and fraction of patients defined as strongly positive change as a function of increasing cut-offs and whether there is evidence for a relative improvement in clinical utility relative to the 1% CPS cut-off. A PD-L1 strongly positive cut-off that maintains high NPV (e.g. near or above 90%) while achieving meaningful enrichment of response and largely capturing patients showing durable clinical benefit is sought. The profiles of PPV, NPV, and the percentage of patients above a given cut-off along with intervals quantifying the uncertainty in those profiles will be estimated as a function of potential cut-offs. Receiver operating characteristic curve analysis will also be used to understand the sensitivity and specificity profile and examine cut-offs that might be suggested based on the ROC curve and their appropriateness with regard to PPV and NPV. CPS ranges for any promising cut-offs will also have to be gauged in the context of practical implementation and interpretation by pathologists in clinical practice.

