#### 8.2.7 Sample Size and Power Calculation

The sample size is driven by the primary efficacy estimation for PD-L1 strongly positive subjects. [Table 9](#) and [Table 10](#) shows 95% CIs at different true ORR rates (number of events), for 60 and 75 PD-L1 strongly positive subjects, respectively.

**Table 9** Estimates and 95% CIs with 60 PD-L1 Strongly Positive Subjects

Sample Size	Number of ORR Event	Proportion	Lower Limit	Upper Limit	Width of 95% CI
60	12	0.2	0.108	0.323	0.215
60	13	0.217	0.121	0.342	0.221
60	14	0.233	0.134	0.36	0.227
60	15	0.25	0.147	0.379	0.231
60	16	0.267	0.161	0.397	0.236
60	17	0.283	0.174	0.414	0.24
60	18	0.3	0.188	0.432	0.244
60	19	0.317	0.203	0.45	0.247
60	20	0.333	0.217	0.467	0.25
60	21	0.35	0.231	0.484	0.253
60	22	0.367	0.246	0.501	0.255

**Table 10** Estimates and 95% CIs with 75 PD-L1 Strongly Positive Subjects

Sample Size	Number of ORR Event	Proportion	Lower Limit	Upper Limit	Width of 95% CI
75	20	0.267	0.171	0.381	0.21
75	21	0.280	0.182	0.396	0.214
75	22	0.293	0.194	0.41	0.216
75	23	0.307	0.205	0.424	0.219
75	24	0.320	0.217	0.438	0.221
75	25	0.333	0.229	0.452	0.223
75	26	0.347	0.24	0.465	0.225
75	27	0.360	0.252	0.479	0.227
75	28	0.373	0.264	0.493	0.229
75	29	0.387	0.276	0.506	0.23
75	30	0.400	0.288	0.52	0.232

Up to 350 subjects will be enrolled. Assuming a 33% prevalence rate of PD-L1 strongly positive subjects and 100 for biomarker discovery population, there is 88% chance to have at least 75 PD-L1 strongly positive subjects and 99.9% chance to have at least 60 PD-L1 strongly positive subjects in the confirmation group.

For all and PD-L1 positive subjects, the expected sample sizes (350 and 225, respectively) are adequate for efficacy estimation. Thus, if strongly PD-L1 positive cannot be determined, the study may stop enrollment after ~225 subjects are enrolled.

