### **8.2.9 Interim Analyses**

A biomarker analysis is planned where data from a subset of subjects (the biomarker discovery population) will be used to determine the PD-L1 strongly positive cut-point. The biomarker discovery population consists of the evaluable subjects among the first 100 subjects enrolled into the study. Analysis will be conducted according to the SAP (section 8.2.5.3). More subjects may be allocated to the biomarker discovery population, if necessary.

In addition, an interim efficacy evaluation for the PD-L1 negative population will be performed using the biomarker discovery population data. Enrollment of PD-L1 negative (CPS  $< 1\%$ ) population may be stopped if the ORR is low and substantial enrollment remains. The futility analysis will be based on the evaluable PD-L1 negative subjects in the biomarker discovery population (up to the first 25 subjects). If the number of PD-L1 negative subjects in the biomarker subgroup is less than 20, additional PD-L1 negative subjects may be included until the number reaches at least 20. The non-binding rule for futility is the upper limit of the 95% CI (two-sided) of the ORR estimate is less than 20% (need at least 1 response in  $N < 26$  subjects, and at least 2 responses in  $N = 26$  to 40 subjects).

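### The PD-L1-negative futility look is limited to 25 subjects yet has counts for N = 26 to 40; if 25 is a hard cap, it stops only at zero responses, and using all evaluable negatives would raise its chance of stopping

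*Combined protocol and SAP*

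**What the plan says.** Section 8.2.9 (Interim Analyses) uses discovery-population data to decide whether enrollment of PD-L1 negative subjects (CPS below 1%) may stop. On the number of subjects: "The futility analysis will be based on the evaluable PD-L1 negative subjects in the biomarker discovery population (up to the first 25 subjects". If fewer than 20 are available, "additional PD-L1 negative subjects may be included until the number reaches at least 20". On the criterion: "The non-binding rule for futility is the upper limit of the 95% CI (two-sided) of the ORR estimate is less than 20" percent. The parenthesis that follows turns this into counts for continuing: "need at least 1 response in" N < 26 subjects, "and at least 2 responses in" N = 26 to 40.

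The interval method for this look is not named. Section 8.2.5.1 computes the primary ORR interval "using an exact binomial distribution (Clopper and Pearson method").

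Section 8.2.4.3 draws the discovery population from the first 100 enrolled. Evaluable subjects are treated subjects with week 9 and week 15 scans, or with progression or death before week 15. No evaluable fraction is given. For all subjects and PD-L1 positive subjects, section 8.2.7 says "the expected sample sizes (350 and 225, respectively) are adequate for efficacy estimation".

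**The concern.** The limit of 25 and the count for N = 26 to 40 cannot both operate: if 25 is the most that can enter, the second count is never used. The choice matters because 25 is one subject short of the size at which a single response is still compatible with stopping. Under a hard cap, one response among the first 25 negatives keeps that stratum open, whatever later negatives in the same discovery data show.

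The look exists to limit further enrollment of a group with little activity. After the first 100 subjects up to 250 remain, and at the implied prevalence that is up to 250 × 125/350 ≈ 89 more negatives.

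**Working it through.** **Inputs.**
- Criterion, limit of 25, floor of 20 and printed counts: section 8.2.9.
- Clopper-Pearson interval: named in section 8.2.5.1 for the primary ORR, assumed here for the futility look.
- Negative prevalence: 1 − 225/350 = 125/350 = 35.7%, derived from section 8.2.7.
- Evaluable number among the first 100: not given; 70, 85 and 100 are assumed.
- True ORR: 5% is illustrative. The plan gives no design value for a low ORR.

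**Step 1: reproduce the printed counts.** The upper limit for x responses in N is the 0.975 quantile of Beta(x + 1, N − x). Stopping needs it below 20%.

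| x/N | Upper limit | Criterion met |
|---|---|---|
| 0/25 | 13.7% | yes |
| 1/25 | 20.35% | no |
| 1/26 | 19.6% | yes |
| 2/33 | 20.2% | no |
| 2/34 | 19.7% | yes |
| 2/40 | 16.9% | yes |
| 3/40 | 20.4% | no |

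The largest number of responses that still stops is 0 for N = 17–25, 1 for N = 26–33 and 2 for N = 34–40. The printed count for N < 26 and the change at 26 therefore reproduce. The printed count for 26–40 holds only up to 33; from 34 to 40 the criterion requires at least 3 responses to continue. Other intervals do not explain this: Wilson limits change at 25 and 33, Agresti-Coull at 27 and 35.

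**Step 2: how many negatives to expect.** 70 × 0.357 = 25.0; 85 × 0.357 = 30.4; 100 × 0.357 = 35.7.

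**Step 3: chance of stopping at a true ORR of 5%.** With exactly 25 negatives, stopping needs zero responses: 0.95^25 = 27.7% (at N = 20, 0.95^20 = 35.8%). In general, take K negatives ~ Binomial(evaluable, 125/350) and N = max(K, 20), cut to 25 under the cap. Then average P(X ≤ c_N), where X ~ Binomial(N, 0.05) and c_N is the largest stopping count.

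| Evaluable | P(at least 26 negatives) | Cap of 25 | All negatives, exact limit | All negatives, printed counts |
|---|---|---|---|---|
| 70 | 45% | 30% | 44% | 43% |
| 85 | 86% | 28% | 57% | 51% |
| 100 | 98% | 28% | 68% | 54% |

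The last column applies the exact limit above N = 40, where no count is printed. If the count of 2 is carried on past 40, the range for 85–100 evaluable becomes 46–50%.

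At fixed N the exact rule moves in steps: 55.4% at 30, 50.4% at 33, 75.9% at 34, 73.2% at 36.

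**Step 4: other true ORRs (85–100 evaluable).**

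| True ORR | Cap of 25 | All negatives, exact limit |
|---|---|---|
| 10% | 7% | 20–26% |
| 15% | about 2% | 5.5–7% |
| 20% | 0.4% | 1.3–1.4% |

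**The case against.** **The cap is only one reading.** The count for N = 26 to 40, and the provision that more subjects may be allocated to the discovery population, suggest that a larger N was contemplated. This stands, and it is why the point is a conflict to be resolved.

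**The contrast depends on assumptions.** This also stands. At 70 evaluable the gap is 30% against 44%. The choice of 5% matters too: even the capped look stops 78% of the time at a true ORR of 1% and 60% at 2%.

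**A cautious look is defensible.** The rule is non-binding, ORR in all subjects is the first-listed primary objective, and stopping negatives would change that population's PD-L1 mix. This is a fair reason to keep false stops rare. They stay rare: 1.3–1.4% at 20%.

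**Waiting may cost time.** Section 8.2.9 does not say when the look takes place. Twenty-five negatives are expected after about 25/0.357 = 70 evaluable subjects, so if an earlier look is intended, using all negatives delays it. If the look waits for the complete discovery data, nothing is lost.

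**A stronger argument that fails.** A reader might infer from section 8.2.5.3, which seeks "high NPV (e.g. near or above 90" percent, that the plan itself calls a 10% response rate low and that the capped look fails at that rate. That text concerns a strongly positive cut-off above CPS 1%. The group below such a cut includes PD-L1 positive subjects. The only threshold stated for this look is 20%.

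**Conclusion.** Section 8.2.9 contradicts itself on the maximum N, and its count for N = 34–40 does not match its own criterion under exact limits. If 25 is a hard cap, the look stops only at zero responses and fires 28–30% of the time at a true ORR of 5%. Using all evaluable negatives would give 57–68% with the exact limit or 51–54% with the printed counts (85–100 evaluable), and 44% or 43% at 70 evaluable. These figures rest on the 35.7% negative prevalence, the assumed evaluable numbers and Clopper-Pearson limits.

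A reader might go further and conclude that the plan certainly discards available negatives and so falls short of its intended chance of stopping. The documents do not support that: they print a count for larger N, give no evaluable fraction and state no target stopping probability. What remains is an inconsistency to reconcile and an inexpensive gain in the look's ability to stop.

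**What to change.** In section 8.2.9:

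1. Base the look on all evaluable PD-L1 negative subjects in the discovery population, keeping the minimum of 20, and remove the limit of 25.
2. Name the Clopper-Pearson interval and state that the upper-limit criterion governs at the N obtained.
3. Correct the counts for continuing: at least 1 response for N < 26, at least 2 for N = 26–33, at least 3 for N = 34–40. Above 40, read the count from the criterion.

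Item 1 alone is not enough, because it moves the look into the range where the printed counts and the criterion disagree. If a hard cap of 25 is intended, say so, give the reason and delete the count for 26–40.

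The cost is a short edit to one section and no extra subjects. The chance of meeting the non-binding rule rises from about 0.4% to 1.3–1.4% at a true ORR of 20%, and from about 2% to 5.5–7% at 15% (85–100 evaluable). The look comes later only if it was meant to precede the complete discovery data.

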### **8.1.4 Biomarker/Interim Analysis**

The biomarker analysis to establish the PD-L1 strongly positive cutpoint is planned. An interim futility analysis is planned for the PD-L1 negative population within the biomarker discovery population. See 8.2.9 for more details.

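### The PD-L1 negative futility counts in SAP 8.2.9 do not match the stated confidence-interval rule for N = 34 to 40, and the N = 26 to 40 band conflicts with the 25-subject cap

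*Combined protocol and SAP*

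**What the plan says.** Section 8.2.9 plans an interim efficacy look at PD-L1 negative subjects (CPS below 1%) within the biomarker discovery population. Enrollment of negatives may be stopped if the response rate is low and substantial enrollment remains.

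- **Criterion:** "The non-binding rule for futility is the upper limit of the 95% CI (two-sided) of the ORR estimate is less than 20" percent.
- **Translation into counts, in parentheses after the criterion:** "need at least 1 response in" fewer than 26 "subjects, and at least 2 responses in" 26 to 40.
- **Analysis set:** evaluable negatives in the discovery population, "up to the first 25 subjects". If there are fewer than 20, "additional PD-L1 negative subjects may be included until the number reaches at least 20".

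Section 8.2.9 does not name the interval method. Section 8.2.5.1 does so for the primary endpoint: the ORR estimate and interval "will be provided using an exact binomial distribution (Clopper and Pearson method"). Section 8.1.4 summarizes the look without giving a sample size: "An interim futility analysis is planned for the PD-L1 negative population within the biomarker discovery population". Section 8.2.7 gives the expected numbers from which a share of negatives can be inferred: "For all and PD-L1 positive subjects, the expected sample sizes (350 and 225, respectively) are adequate for efficacy estimation".

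**The concern.** The paragraph gives one decision rule in two forms, an interval and a table of counts, and they should agree at every N the table covers. A single minimum of two responses across N = 26 to 40 is suspect. The upper limit for a fixed number of responders falls steadily as N grows, and this range looks too wide for one count to serve.

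The second problem is the range itself. With a cap of 25 and a top-up meant only to reach 20, planned N runs from 20 to 25. A band for 26 to 40 then has no use, and its presence suggests that a larger analysis set was also in mind.

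This is the only numerical criterion the plan gives for stopping enrollment of PD-L1 negative subjects. If more than 25 negatives are on hand, the analyst cannot tell from the text which N to use. At some N the two forms of the rule give opposite answers.

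**Working it through.** **Method.** The Clopper-Pearson two-sided 95% upper limit for x responders in N is the 0.975 quantile of Beta(x + 1, N − x). The matching lower limit is the 0.025 quantile of Beta(x, N − x + 1). As a check, these reproduce Tables 9 and 10 of section 8.2.7: 12/60 gives 0.108 to 0.323, 18/60 gives 0.188 to 0.432, and 20/75 gives 0.171 to 0.381, all as printed.

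**Upper limits around each change of count** (criterion met if below 0.20):

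| Responders | Last N not meeting it | First N meeting it |
|---|---|---|
| 0 | N = 16: 0.2059 | N = 17: 0.1951 |
| 1 | N = 25: 0.2035 | N = 26: 0.1964 |
| 2 | N = 33: 0.2023 | N = 34: 0.1968 |
| 3 | N = 40: 0.2039 | N = 41: 0.1992 |

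The minimum number of responses needed to avoid futility is therefore:

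- 1 for N = 17 to 25
- 2 for N = 26 to 33
- 3 for N = 34 to 40

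The plan's outer edges, 25/26 and 40, fall exactly on Clopper-Pearson change points. That supports reading 8.2.9 with this method. Only the change at 33/34 is missing. Above it, two responders give 0.1866 at N = 36 and 0.1692 at N = 40, clearly below 0.20.

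**Other interval methods.** The range of N over which exactly two responses are needed is 25 to 32 for Wilson, 27 to 34 for Agresti-Coull and 22 to 29 for Jeffreys. For Wald it ends at 23. None covers 26 to 40.

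**Within the cap.** For N = 20 to 25 the interval and the count agree: only zero responders meets the criterion. The probability of meeting it is (1 − p)^N.

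| True ORR p | N = 20 | N = 25 |
|---|---|---|
| 2% | 67% | 60% |
| 5% | 36% | 28% |
| 10% | 12% | 7% |

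**If N may exceed 25.** From 8.2.7 the implied negative share is (350 − 225)/350 = 125/350 = 35.7%. Assuming the first 100 subjects have the same mix, the expected number of negatives is 35.7 with 100 evaluable, 32.1 with 90 and 28.6 with 80. At N = 36, with X binomial(36, p):

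| True ORR p | Interval rule, P(X ≤ 2) | Printed count, P(X ≤ 1) | Disagreement, P(X = 2) |
|---|---|---|---|
| 5% | 73.2% | 45.7% | 27.5% |
| 10% | 28.8% | 11.3% | 17.5% |

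**Chance of reaching the faulty range with no cap.** Treating the number of negatives as binomial with share 125/350, the probability that N lies in 34 to 40 is about 12%, 34% and 52% with 80, 90 and 100 evaluable. Multiplying by the probability of exactly two responders at N = 36 gives the approximate overall chance that the two forms disagree:

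- At a true ORR of 5%: 0.12 × 0.275 ≈ 3%, 0.34 × 0.275 ≈ 9%, 0.52 × 0.275 ≈ 14%.
- At a true ORR of 10%: 0.12 × 0.175 ≈ 2%, 0.34 × 0.175 ≈ 6%, 0.52 × 0.175 ≈ 9%.

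**The case against.** The strongest reply is that the error never operates. If the cap of 25 is applied, one response is the correct minimum and the second count is surplus text. If the cap is not applied, the band is not redundant, so the two faults cannot both bite. The interval sentence is also the stated rule, with the counts only a gloss on it, and a stated minimum of two does not strictly say that two suffices. The rule is non-binding and the trial is one of estimation. The N = 36 figures need the cap set aside and all 100 subjects evaluable; with 80 or 90 evaluable the expected N is 29 or 32, where the printed count is right.

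Most of this stands as a limit on weight. The probabilities above are chances that the criterion is met, not that enrollment stops, and the overall chance of disagreement is well below the N = 36 figures. The absence of a cap in 8.1.4 adds nothing either, since that section is a summary that refers to 8.2.9.

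It does not rescue the text. The parenthesis exists to tell the analyst what count the rule implies, and it tells them wrongly for seven of the fifteen values of N in its upper band. On the 35.7% share, more than 25 negatives would be available with probability about 76%, 93% or 99% for 80, 90 or 100 evaluable subjects. The conflict between cap and band would therefore probably have to be resolved in practice.

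**Conclusion.** The concern holds on both parts. The printed counts are right for N = 17 to 33 and wrong for N = 34 to 40, where three responses are needed. The band for N = 26 to 40 also contradicts the 25-subject limit in the same paragraph.

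The practical reach is modest. With the cap observed, the count error has no effect. Without it, the two forms of the rule differ only at exactly two responders when N is 34 to 40. What is affected is a discretionary, non-binding decision on further PD-L1 negative enrollment; no hypothesis test or error rate depends on it.

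The change points assume Clopper-Pearson, which 8.2.9 does not name but which its own break at 25/26 reproduces. The figures for N above 25 also assume that the first 100 subjects have the 125/350 negative share implied by 8.2.7, which the documents do not state for that group.

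**What to change.** Revise the parenthesis in 8.2.9 in one of two ways. The choice of N is the sponsor's.

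1. **Keep the cap.** Delete the count for N = 26 to 40 and keep one response as the minimum for N = 20 to 25.
2. **Allow N above 25.** Remove the cap and print the minimum as 1 for N = 17 to 25, 2 for N = 26 to 33 and 3 for N = 34 to 40. Give the probability of meeting the criterion at the intended N.

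Under either option, state that the two-sided 95% Clopper-Pearson upper limit governs if a count and the interval disagree. Replace the open lower range (N below 26) with an explicit lower bound: at N = 16, zero responders give an upper limit of 20.6% and do not meet the criterion. That case arises only if the optional top-up to 20 is not made.

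The cost is one or two sentences, with no added subjects and no added look. Option 2 carries a trade-off that should be stated: at a true ORR of 10%, the chance of meeting the futility criterion rises from 7% at N = 25 to 29% at N = 36.

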### **8.2.10 Compliance (Medication Adherence)**

A day within the study will be considered an On-Therapy day if the subject receives the study medication infusion. The number of Days on Therapy is the total number of days from the first day of study medication to the date of the last dose of study medication.

Summary statistics for the number of Days on Therapy will be provided by treatment group for the APT population.

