### **5.8.2 Discontinuation of Study Therapy after CR**

Discontinuation of treatment may be considered for subjects who have attained a confirmed CR that have been treated for at least 24 weeks with pembrolizumab (MK-3475) and had at least two treatments with pembrolizumab (MK-3475) beyond the date when the initial CR was declared. Subjects who then experience radiographic disease progression may be eligible for up to one year of additional treatment with pembrolizumab (MK-3475) at the discretion of the investigator if no cancer treatment was administered since the last dose of pembrolizumab (MK-3475), the subject meets the safety parameters listed in the Inclusion/Exclusion criteria, and the trial is open. Subjects will resume therapy at the same dose and schedule at the time of initial discontinuation. Additional details are provided in Section 7.1.5.2.1. Response or progression in this Second Course Phase will not count towards the ORR as the primary endpoint in this trial.

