##### **7.1.5.2.1 Second Course Phase (Retreatment Period)**

Subjects who stop pembrolizumab (MK-3475) with SD or better may be eligible for up to one year of additional pembrolizumab (MK-3475) therapy if they progress after stopping study treatment. This retreatment is termed the Second Course Phase of this study and is only available if the study remains open and the subject meets the following conditions:

- **Either**
  - Stopped initial treatment with pembrolizumab (MK-3475) after attaining an investigator-determined confirmed CR according to RECIST 1.1
    - Was treated for at least 24 weeks with pembrolizumab (MK-3475) before discontinuing therapy
    - Received at least two treatments with pembrolizumab (MK-3475) beyond the date when the initial CR was declared

**OR**

- Subject had SD, PR or CR and stopped pembrolizumab (MK-3475) treatment after 24 months of trial treatment for reasons other than disease progression or intolerability

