**AND**

- Experienced an investigator-determined confirmed radiographic disease progression after stopping their initial treatment with pembrolizumab (MK-3475)
- Did not receive any anti-cancer treatment since the last dose of pembrolizumab (MK-3475)
- Have a performance status of 0 or 1 on the ECOG Performance Scale
- Demonstrate adequate organ function as detailed in Section 5.1.2
- Female subject of childbearing potential should have a negative urine or serum pregnancy test within 72 hours prior to receiving retreatment with study medication.
- Female subjects of childbearing potential should be willing to use 2 methods of birth control or be surgically sterile, or abstain from heterosexual activity for the course of the study through 120 days after the last dose of study medication (Reference Section 5.7.2). Subjects of child bearing potential are those who have not been surgically sterilized or have been free from menses for > 1 year.

Note: Abstinence is acceptable if this is the usual lifestyle and preferred contraception for the subject.

- Male subjects should agree to use an adequate method of contraception starting with the first dose of study therapy through 120 days after the last dose of study therapy.

Note: Abstinence is acceptable if this is the usual lifestyle and preferred contraception for the subject.

- Does not have a history or current evidence of any condition, therapy, or laboratory abnormality that might interfere with the subject's participation for the full duration of the trial or is not in the best interest of the subject to participate, in the opinion of the treating investigator.

Subjects who restart treatment will be retreated at the same dose frequency as when they last received pembrolizumab (MK-3475). Treatment will be administered for up to one additional year.

Visit requirements are outlined in Section 6.0 – Trial Flow Chart.

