### **8.2.11 Extent of Exposure**

Extent of Exposure for a subject is defined as number of cycles in which the subject receives the study medication infusion. Summary statistics will be provided on Extent of Exposure for the APT population.

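### Days on Therapy in Section 8.2.10 runs from first to last dose, so as written it counts the off-drug interval before a Second Course as therapy

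*Combined protocol and SAP*

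**What the plan says.** Section 8.2.10 of the combined protocol and SAP contains three relevant statements.

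- An On-Therapy day: "A day within the study will be considered an On-Therapy day if the subject receives the study medication infusion".
- The number of Days on Therapy: the "total number of days from the first day of study medication to the date of the last dose of study medication".
- Reporting: "Summary statistics for the number of Days on Therapy will be provided by treatment group for the APT population".

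Section 8.2.11 gives a second measure, Extent of Exposure, "defined as number of cycles in which the subject receives the study medication infusion".

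Treatment may stop and later restart. Section 5.8.2 covers subjects who stop after a confirmed complete response: "Subjects who then experience radiographic disease progression may be eligible for up to one year of additional treatment". Section 7.1.5.2.1 opens retreatment to subjects who stop with stable disease or better, "if they progress after stopping study treatment". Two routes lead there: stopping for complete response after at least 24 weeks of treatment, or stopping at 24 months with SD, PR or CR.

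The same section fixes the status of the second course: "This retreatment is termed the Second Course Phase of this study and is only available if the study remains open". Its list of conditions includes a pregnancy test "prior to receiving retreatment with study medication", so the retreatment drug is called study medication. The one analysis from which the documents exclude the Second Course is ORR (Section 5.8.2).

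**The concern.** A subject who stops, is followed off drug until progression and then restarts has two treatment courses with a gap between them. A single span from the first dose of the first course to the last dose of the second includes that gap.

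The protocol itself treats the gap as off treatment. Section 7.1.4.1 sends these subjects to a Safety Follow-up Visit and then to the Follow-up Period, and Section 7.1.5.3.1 allows a separate safety visit after each course. Under the flow chart notes, all adverse events are recorded only to 30 days after the last dose. SAEs and ECIs are reported to 90 days at most, and after that only if related. So 8.2.10 would count as therapy many days on which non-serious events are not collected.

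At stake is the accuracy of a planned summary of treatment duration, chiefly its upper tail and maximum. A second, smaller problem is that the sentence before the definition ties an On-Therapy day to an infusion, which does not match a calendar span.

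**Working it through.** The plan states no figure for Days on Therapy, so there is nothing to reproduce. The check applies the 8.2.10 rule to dosing calendars.

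**Inputs from the documents**
- Dosing every 21 days (Section 5.2).
- First course: 24 weeks (168 days) as the minimum on the complete-response route, or 24 months (730 days) from first dose (Sections 7.1.5.2.1 and 5.8).
- Second Course: up to one year (Section 7.1.5.2.1).
- 350 subjects (Section 8.2.7).

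**Assumptions (the documents give none of these)**
- Gap from the last first-course dose to the first Second Course dose: 91, 182 or 365 days.
- Second Course of 63 or 365 days.
- 3 to 20 subjects retreated.
- Both end days are counted.

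**Formulas**
- Span as written = last dose of the Second Course − first dose of the first course + 1.
- Sum of courses = (last − first + 1) for each course, added.
- Excess = span − sum = gap − 1.

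**One case in full.** The 24-week course has doses on days 0 to 168: 9 doses, 169 days. A one-year Second Course has its last dose 357 days after its first: 18 doses, 358 days. With a 182-day gap:
- span = 168 + 182 + 357 + 1 = 708 days;
- sum = 169 + 358 = 527 days;
- excess = 181 days, and 181/527 = 34%.

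**All cases** (days under 8.2.10, with the excess as a percentage of the sum)

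| First + Second Course | Sum of courses | Gap 91 | Gap 182 | Gap 365 | Doses |
|---|---|---|---|---|---|
| 24 weeks + 63 days | 233 | 323 (+39%) | 414 (+78%) | 597 (+156%) | 13 |
| 24 weeks + 365 days | 527 | 617 (+17%) | 708 (+34%) | 891 (+69%) | 27 |
| 24 months + 63 days | 779 | 869 (+12%) | 960 (+23%) | 1143 (+47%) | 39 |
| 24 months + 365 days | 1073 | 1163 (+8%) | 1254 (+17%) | 1437 (+34%) | 53 |

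The excess is 90, 181 or 364 days in every row. The number of doses, which is what 8.2.11 counts, does not depend on the gap.

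**Effect on the overall mean** = number retreated × (gap − 1) / 350.
- Low end: 3 × 90 / 350 = 0.8 days.
- High end: 20 × 364 / 350 = 20.8 days.

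**Median.** Adding the gap moves the median only if it carries a retreated subject from below the median to above it. With at most 20 of 350 retreated, each having at least 24 weeks of first-course treatment, little or no movement is expected.

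**The infusion-day sentence.** A 24-month course has 35 infusion days (doses on days 0 to 714) against a span of 715 days. The two sentences describe different quantities.

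**The case against.** The strongest reply is that 8.2.10 does not say whether Second Course doses enter this summary, and that the protocol handles that course separately elsewhere: its own flow chart, its own safety visit, exclusion from ORR. If only the initial course was meant, the overstatement disappears. That is true, but no such limit is written. With retreatment called a phase of this study and its drug study medication, and with ORR the only stated exclusion, the rule as written takes those doses in.

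Several stronger readings are tempting and should be set aside.

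- A reader might infer that the inflated duration makes the drug look better tolerated. Section 8.2.5.2 plans counts, percentages and confidence intervals for incidence rates. No exposure-adjusted rate is specified, and nothing in Section 8 divides by Days on Therapy.
- A reader might infer that only long responders are affected. Subjects who complete 24 months with stable disease can also be retreated. Within-course interruptions (Sections 5.2.1.2 and 7.1.1.8) are counted for anyone.
- A reader might infer that the two sentences in 8.2.10 leave the reported quantity undefined. Only the number of Days on Therapy is summarised, and it has its own definition. The infusion-day sentence is unused.

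Two further points against the finding stand. Section 8.2.11 already supplies an exposure measure that a gap cannot inflate. The longest examples also strain the calendar: four of the six 24-month cases exceed the roughly 36 months estimated for the whole trial in Section 1.0, and retreatment requires the study to be open. The document history, from August 2014 to May 2021, suggests a longer trial, so those cases are not excluded. All six 24-week cases fit within 36 months (the longest is 168 + 365 + 365 = 898 days, about 29.5 months).

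**Conclusion.** The point holds as a minor one. Followed literally, 8.2.10 reports off-drug time as therapy for any retreated subject. The excess is essentially the gap itself, and the relative overstatement in the cases above is 8% to 156% for the individual subject. Across the trial the effect on the mean is small, the median is close to unaffected, and the maximum and upper tail carry most of the distortion.

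The direction follows from the definition. The size rests on assumed gap lengths, Second Course lengths and numbers retreated. No efficacy or safety conclusion depends on this summary.

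**What to change.** In 8.2.10:

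1. Define Days on Therapy per course as last dose − first dose + 1.
2. Report the initial course as the main summary, and report the Second Course and the sum of the two separately.
3. Delete the infusion-day sentence or align it with the span definition.

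This is an edit of one or two sentences. It needs no new assessments, since drug administration is scheduled by cycle in both flow charts (Sections 6.1 and 6.2). The documents do not describe the database, so it is an assumption that dose dates can be assigned to a course.

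The cost is a slightly shorter reported duration. For a retreated subject the main figure also leaves out the Second Course: in the worked case it is 169 days, with 358 and 527 shown alongside. Interruptions within a course would still be counted, and the text should say so.
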